**Figure 2. Participant Flow Diagram**

**Overview of Study Design.** Our primary aim is to analyze the efficacy of the 6-month REAL-T intervention in a large-scale two-arm RCT. To achieve this aim, N=210 YAs with T1D will be randomized evenly to two conditions: REAL-T or usual care control. The primary outcome is A1c, with key secondary outcomes pertaining to psychosocial well-being (depressive symptoms, diabetes distress, and DQoL). In addition, we will examine the effects of REAL-T after 3- and 6-month no-treatment follow-up periods. Furthermore, we will analyze mediating mechanisms of the intervention's effects on outcomes through structural equation modeling, and conduct exploratory analyses to evaluate the cost-effectiveness, cost impact, and change in QALYs associated with the REAL-T intervention relative to usual care. Quarterly data collection visits, performed over a 12-month period, will enable longitudinal modeling of changes in glycemic control, psychosocial well-being, and other primary and secondary endpoints. In addition, blinded CGM data collected at baseline, 6 months (immediately post-intervention), and 12 months (long-term follow-up) will facilitate a more robust analysis of the impact of the REAL-T intervention on glycemic control, through

an examination of changes in glycemic variability, percent time in range, percent time in hypoglycemia, and percent time in hyperglycemia. Figure 2 provides an overview of data collection throughout the study period.

**Participants.** Eligibility criteria, as outlined in Table 3, were chosen to ensure a medically stable pool of participants and maximize the potential of therapeutic benefit. In addition, the intervention is most appropriate for those with demonstrated diabetes care challenges and risk of developing complications, as evidenced by an elevated A1c level. Because of key differences in the pathophysiology and management of T1D and T2D, we have elected to restrict participation to YAs with T1D only.

To verify eligibility, we need to confirm A1C. Estimated A1C will be used for initial enrollment, and verified through A1C test results received from our laboratory. Estimated A1C will be identified through: (1) recent A1C from participant's medical records (directly from EMR or self-report); (2) GMI (estimated A1c) from participant's CGM software; or (3) participant self-reports that A1C has consistently been >7.5%.

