Healthcare utilization		Study-specific survey; medical record reviews	Incidence of diabetes-related outpatient medical visits, ED visits, urgent care visits, hospitalizations	Monthly				

**Data Management and Analysis.** The study's analytic plan is outlined in brief in this section; for further details, please refer to the "Statistical Design and Power" attachment in the PHS Human Subjects and Clinical Trials Information section. **Data Management:** Data will be uploaded and stored in a REDCap database management system. REDCap is a secure, web-based application designed to support data capture for research studies, providing an intuitive interface for validated data entry. It also includes audit trails for tracking data manipulation and export procedures; automated export procedures for seamless data downloads to common statistical packages; and procedures for importing data from external sources. The REDCap website is password-protected and restricted to authorized users (See Data and Safety Monitoring Plan). Research assistants will enter and reconcile all data, with further data quality checks performed by the biostatistician. Prior to conducting hypothesis tests, baseline participant characteristics will be described using frequency distributions, histograms, and summary statistics. Sparse data may be recoded to dichotomous or ordinal data.

**Power and Sample Size:** The study is powered for an intention-to-treat analysis of our primary outcome, change in A1c over the intervention period (including 3 and 6-month data). Other analyses are designated as secondary,

**Table 6. Power, given 210 participants, for testing intervention effects on A1c over 6 months (Aim 1), 9 and 12 months (Aim 2), and mediators/secondary outcomes (Aim 3).**

A1c 0-6 months (Aim 1)			A1c 0-9 or 0-12 months (Aim 2)			SEM/mediation analysis (Aim 3)		
% $\Delta$	Effect size	6-month attrition	% $\Delta$	Effect size	Annual attrition	Effect size (path a/path b)	6-month attrition	
0.81	0.55	>.99	0.81	0.55	>.99	.26/.36	.95	.95
0.59	0.40	.93	0.59	0.40	.97	.36/.26	.92	.92
0.50	0.34	.82	0.50	0.34	.89	.26/.26	.89	.88

to control the type 1 error rate in identifying statistically significant changes in the primary outcome. Power analyses were conducted using proc glmpower in SAS using a 2-sided alpha of 0.05. As described comprehensively in the "Statistical Design and Power" attachment, we calculated power for a range of

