**Cost Analyses:** We will evaluate the cost-effectiveness, cost impact, and change in quality-adjusted life years (QALYs) associated with REAL-T relative to usual care. We will calculate incremental cost-effectiveness ratios (ICERs) divided by the average difference in QALYs; if preliminary analyses demonstrate that REAL-T is both cost-saving and net health beneficial (which would render the ICERs moot), we will instead calculate the projected total net health benefits for REAL-T relative to usual care. ICERs will be calculated according to generally recognized best practices, using two different timeframes and scopes. The first will be a simple Cost Utility Analysis (CUA) over a 12-month timeframe, using cost and QALY inputs derived directly from observed data, adopting a “Payer” perspective (direct medical costs only). This CUA estimate will likely represent a conservative lower bound, given the short follow-up period, as the greatest intervention costs are incurred up-front, while some medical cost savings may take longer to realize. The second CUA will employ modeling to project longer-term costs and health benefits, using parameter estimates derived from the literature, from both a “Payer” perspective and a “Social Planner” perspective (direct and indirect medical costs). The mathematical approach will employ Markov modeling, but may also incorporate microsimulation, decision trees, or Monte Carlo methods. Non-parametric bootstrapping methods will be used to bound the ICER estimates by deriving confidence intervals around the cost-effectiveness ratios for the 12-month timeframe CUA. For the longer-term CUA, we will conduct univariate and multivariate sensitivity analyses to further bound the ICER estimates.

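### Low severity: in the exploratory 12-month cost-utility analysis, ICER limits become hard to read if bootstrap QALY differences straddle zero; add net benefit and a plane or acceptability curve from the same replicates

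*Combined protocol and SAP*

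**What the plan says.** The Overview of Study Design says the team will "conduct exploratory analyses to evaluate the cost-effectiveness, cost impact, and change in QALYs associated with the REAL-T intervention relative to usual care". The Cost Analyses paragraph plans two cost-utility analyses. The first covers 12 months, "using cost and QALY inputs derived directly from observed data, adopting a “Payer” perspective (direct medical costs only"). Its uncertainty is described in one sentence: "Non-parametric bootstrapping methods will be used to bound the ICER estimates by deriving confidence intervals around the cost-effectiveness ratios". The longer-term modelled analysis has its own sensitivity analyses and is outside this point.

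Net health benefit replaces the ICER "if preliminary analyses demonstrate that REAL-T is both cost-saving and net health beneficial". No interval is tied to that replacement. The paragraph also promises to evaluate "cost-effectiveness, cost impact, and change in quality-adjusted life years (QALYs) associated with REAL-T relative to usual care", so cost and QALY differences will be seen separately.

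The text names no bootstrap interval method, willingness-to-pay range, cost-effectiveness plane or acceptability curve. It gives no rule for a QALY difference near or below zero. Under Data Management and Analysis, however, the "analytic plan is outlined in brief in this section", and the reader is sent to a Statistical Design and Power attachment that is not among the documents reviewed.

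**The concern.** An ICER is a ratio whose denominator, the QALY difference, may not be clearly different from zero after 12 months. If replicates fall on both sides of zero, the ratio loses its order. A negative value arises when REAL-T is cheaper and better (dominant) and also when it is dearer and worse (dominated). Sorting such replicates and taking limits mixes opposite conclusions.

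The planned move to net health benefit does not cover this. It applies when the result is that REAL-T saves money and improves health. A result of slightly dearer and slightly better keeps the ICER interval, however the replicates scatter. The plan itself makes such a result plausible at 12 months, because it expects intervention costs early and some savings later.

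At stake is how clearly the cost result can be read. Separate cost and QALY summaries show the sign of each difference but not their joint uncertainty.

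**Working it through.** The documents give no QALY difference, QALY SD, cost SD, correlation, threshold or expected ICER, so there is no stated figure to reproduce. The only input from them is "N=210 YAs with T1D will be randomized evenly to two conditions", or 105 per arm. Everything else below is assumed. Money is in dollars.

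**Step 1: how often replicates straddle zero.** SE = SD × √(2/n), with n = 105, or 84 after an assumed 20% loss. With replicates centred on the observed difference, more than 2.5% lie at or below zero when that difference is under 1.96 SE. The chance is Φ(1.96 − δ/SE) for true gain δ. Example: SD .10, n = 105 gives SE = .0138; at δ = .02, Φ(1.96 − 1.449) = Φ(.511) = 70%.

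| True QALY gain | SD .05, n = 105 | SD .10, n = 105 | SD .15, n = 84 |
|---|---|---|---|
| .01 | 70% | 89% | 94% |
| .02 | 17% | 70% | 86% |
| .03 | 1% | 42% | 75% |
| .05 | 0% | 5% | 42% |
| .08 | 0% | 0% | 7% |

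This equals the chance that the QALY difference is not significantly above zero at two-sided .05.

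**Step 2: a case where the limits are hard to read.** Assume 105 per arm, QALY SD .10, cost SD 6,000, independence, and observed differences of +1,000 and +.02 QALY.
- SEs: .10 × √(2/105) = .0138 and 6,000 × √(2/105) = 828.
- ICER = 1,000/.02 = 50,000 per QALY.
- Simple percentile limits, one possible method, by numerical integration of the normal ratio: about −355,000 to +513,000. Simulation agrees within a few thousand.
- 17% of ratios are negative, and 38% of those are dominated (.17 × .38, about 6.5% of all replicates). Φ(−.02/.0138) = 7.4% of replicates have a QALY difference at or below zero.
- Net benefit at 100,000 per QALY: 100,000 × .02 − 1,000 = +1,000. SE = √(1,380² + 828²) = 1,609. The 95% CI is about −2,150 to +4,150, and the probability of being cost-effective is Φ(1,000/1,609) = 73%.
- With cost-QALY correlation −.3, the percentile limits are −475,000 to +628,000 and the probability is 71%. With +.3 they are −256,000 to +405,000 and 77%.

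**Step 3: is this only a fault of percentile limits?** Fieller's 95% set has leading coefficient .02² − 1.96² × .0138² = .000400 − .000732, which is negative, so no finite interval exists. The set is the whole line at correlation 0 and +.3, and two unbounded pieces at −.3.

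**Step 4: cases where the limits behave.** Change only the QALY SD to .05 (SE .0069). Now Φ(−.02/.0069) = 0.2% of replicates are at or below zero, and 1.4% of negative ratios are dominated. Percentile limits are about −36,000 to +213,000 and Fieller limits about −34,000 to +219,000. The negative part now means almost entirely cost-saving with a QALY gain.

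**Step 5: separate check with skewed costs.** A 5,000-replicate bootstrap with gamma-distributed costs (cost SD 5,000, 105 per arm) gave the same picture. With QALY SD .10, +.02 QALY and +500, limits were about −243,000 to +267,000. Replicates lay in all four quadrants: 71% dearer and better, 21.5% cheaper and better, 5.9% dearer and worse, 1.6% cheaper and worse. With QALY SD .05, +.03 QALY and +1,500, limits were about 5,800 to 116,000, with no difficulty.

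**The case against.** The strongest reply is that this is a reporting preference in an exploratory analysis. The bootstrap already produces the joint replicates, and a plane or net-benefit summary only displays them differently. Cost and QALY differences will be shown separately, net health benefit is used under dominance, and the ICERs are to follow accepted good practice. The section is a brief outline, and the attachment may say more. In the Step 2 example only about 7% of replicates have no QALY gain, net benefit is also inconclusive, and a very wide ICER interval would itself warn the reader.

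Most of this stands, and it sets the severity. It does not remove the point. The commitment to good practice concerns calculating ICERs and names none of these outputs. Separate summaries do not give joint uncertainty. A wide interval signals imprecision but does not say how far costs and QALYs together favour either arm; 73% at a stated threshold does.

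Two stronger readings are tempting, and neither is supported. A reader might infer that the ICER interval will fail in this trial. Step 1 runs from about 0% to 94% on assumed inputs, so it does not show that the problem is likely here. A reader might also infer that the planned interval should be dropped. Steps 4 and 5 show cases where it is finite and readable.

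**Conclusion.** The point holds at low severity. As written, the 12-month analysis has one stated uncertainty summary, and that summary cannot be read as an ordered range of cost per QALY if replicate QALY differences straddle zero. Whether they will depends on the size of the QALY gain relative to its SE, which the documents do not give. On the assumptions used, trouble is common at gains of .01 to .02 QALY unless the QALY SD is near .05, and rare at .08. All magnitudes rest on assumed SDs, differences, correlations, attrition and threshold, with normal approximations except in Step 5. The A1c analysis and sample size are untouched, and no data are lost. If the attachment already covers net benefit, a cross-reference would settle the matter.

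**What to change.** Add a few sentences to the Cost Analyses paragraph:

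- From the same bootstrap replicates, and whichever quadrant the estimate falls in, report incremental net benefit with a 95% CI over a prespecified willingness-to-pay range, plus the cost-effectiveness plane or an acceptability curve.
- Keep the planned ICER interval and name its method. Interpret it as a range of cost per QALY only when essentially all replicates have a positive QALY difference, with that cut-off stated in advance. Otherwise give the ICER as a point estimate and rely on net benefit.

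This needs no new data and no further resampling. The one real cost is having to settle a willingness-to-pay range beforehand, which the documents do not currently give.
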